4. 4.1. 4.2. 4.3.1. 4.3.2. 4.4. 4.4.1. 4.4.2. 4.5. 4.5.1. 4.6.1. 4.6.2. 4.6.3. 4.6.4. 4.7. 4.8.1. 4.9.	Statistical Analyses General Considerations Participant Dispositions Primary Endpoint Analysis Definition of endpoint Main analytical approach Secondary Endpoint Analysis Definition of endpoints Main analytical approach Exploratory Endpoints Analysis Summary for the Analysis of Exploratory Measures Safety Analyses Extent of Exposure Adverse Events Product Complaints Additional Safety Assessments Other Analyses Subgroup analyses Interim Analyses Data Monitoring Committee (DMC) or Other Review Board Changes to Protocol-Planned Analyses	.14 .16 .17 .17 .18 .18 .20 .23 .24 .25 .28 .35 .35 .35 .35 .35
5.	Sample Size Determination	.36
6. 6.1. 6.1.1. 6.1.2. 6.2. 6.3.	Supporting Documentation Appendix 1: Demographic and Baseline Characteristics Prior and Concomitant Medications/Therapy Medical History Appendix 2: Treatment Compliance Appendix 3: Search Criteria for Standardized MedDRA Queries	.37 .37 .38 .39 .39
7.	References	.41

Version History

This Statistical Analysis Plan (SAP) for study I8F-MC-GPIL is based on the protocol dated 16AUG2022.

The second version of SAP (SAP V2.0) for study I8F-MC-GPIL incorporates the updates jointly decided by Eli Lilly & Co. and PPD. Please see Revision History for details.

SAP Version History Summary

SAP Version	Approval Date	Change	Rationale
1.0	13 Feb 2023	Not Applicable	Original version
2.0	19 Sep 2023	Post-Dry Run 1 update	

Revision History

The key changes of SAP V2.0 for study I8F-MC-GPIL are summarized below:

- Section 3 (p. 13). Add the definition of inadvertent enroller.
- Section 4.1 (p. 15). Clarify the CGM data from a non-compliant session will be excluded from CGM-related analysis.
- Section 4.5 (p. 22). Remove the formula of mean 24-hour daily blood glucose.
- Section 4.6.2 (p. 25). Explain how the AE of interest is defined.
- Section 6.1.1 (p. 37). Add additional criteria to distinguish prior and con med.
- Section 6.1.1 (p. 38). Defines OAM.
- Section 6.3 (p. 39). List all SMQs requested in the TLF outputs.

1. Introduction

This study aims to investigate the effects of switching from glucagon-like peptide-1 receptor agonist (GLP-1 RA) therapy to tirzepatide in people with type 2 diabetes (T2D). Tirzepatide is a recently approved single molecule that acts as glucose-dependent insulinotropic polypeptide (GIP) and GLP-1 RA, which has demonstrated an ability to reduce HbA1c and body weight in adults with T2D across all 3 therapeutic doses: 5, 10, and 15 mg (Del Prato et al. 2021; Frías et al. 2021; Ludvik et al. 2021; Rosenstock et al. 2021; Dahl et al. 2022).

The study will assess the efficacy and safety characteristics of the study intervention by using a starting dose of 5 mg tirzepatide and will evaluate changes in glycemic control, body weight, and gastrointestinal (GI) tolerability occurring in the first 12 weeks for the targeted study population.

There are no changes to the analyses described in the protocol. Table, figure, and listing specifications are contained in a separate document.

1.1. Objectives, Endpoints, and Estimands

Objectives	Endpoints
Primary	
• To demonstrate that participants with T2D switching from a stable dose of GLP-1 RA to tirzepatide 5 mg QW have an improvement in HbA1c at Week 12 compared to baseline	• Change from baseline in HbA1c
Secondary	
 To evaluate the changes in CGM- assessed TAR from baseline at Week 4 and at Week 12 	 Change from baseline in Percentage of time per day that CGM-derived values are >180 mg/dl (10 mmol/L) Duration of time in minutes per day that CGM-derived values are >180 mg/dl (10 mmol/L)
• To evaluate the change in FSG from baseline at Week 12	• Change from baseline in FSG
• To evaluate the changes from baseline in weight at Week 12	• Change from baseline in weight
Exploratory	

• To evaluate changes in CCM derived	Change from baseline in
• To evaluate changes in COM-derived	
measures from baseline over the	 standard CGM metrics (TIR,
course of 12 weeks	TBR, GV)
	 time in TITR
	 composite of all in-ranges
	 mean 24-hr daily blood
	glucose
	 estimated post-prandial
	glucose excursion
	 estimated fasting glucose
Abbreviations:	

 $CGM = continuous glucose monitoring; FSG = fasting serum glucose; GLP-1 RA = glucagon-like peptide-1 receptor agonist; GV = glycemic variability; HbA1c = hemoglobin A1c; QW = once-weekly; T2D = type-2 diabetes; TAR = time above range (>180 mg/dl or >10 mmol/L); TBR = time below range (<math>\leq$ 70 mg/dl or \leq 3.9 mmol/L); TIR = time-in-range (71 to 180 mg/dL or 3.9 to 10 mmol/L); TITR = time in tight target range (71 to 140 mg/dL or 3.9 to 7.8 mmol/L);

Primary estimand

The primary estimand in this study is the efficacy estimand.

The efficacy estimand focuses on the treatment effect if participants continued to receive the study treatment without prohibited medication. This estimand will be used in publications to inform prescribers or physicians.

The primary clinical question of interest is

What is the change in HbA1c from baseline to Week 12 in participants with T2D, regardless of changes in background oral antihyperglycemic medication (OAM), and assuming that participants continue to take treatment without use of prohibited medication?

This estimand is described by the following attributes:

- Population: participants with T2D on a GLP-1 RA who may benefit from additional therapy. Further details can be found in Protocol Section 5.
- Endpoint: changes from baseline to Week 12 in HbA1c.
- Treatment condition: treatment with tirzepatide regardless of changes to the background OAM. Further details on study treatment can be found in Protocol Section 6.
- Intercurrent events of interest: "Treatment discontinuation for any reason" and "Initiation of prohibited medication" will be addressed using the following strategies:
 - As if participants stay on the treatment (hypothetical strategy)
 - As if participants did not receive prohibited medication (hypothetical strategy).
- Population-level summary: Mean HbA1c change from baseline
- Rationale for estimand: Estimating the effect of study intervention without confounding from prohibited mediations or treatment discontinuation

CONFIDENTIAL

Secondary Endpoints based on Primary Estimand

1) The first clinical question of interest is for the secondary objective regarding continuous glucose monitoring levels:

What is the change in CGM-assessed time above range (TAR) from baseline in participants with T2D, regardless of changes in background OAM, and assuming that participants continue to take treatment without use of prohibited medication?

There are two endpoints defined for the above question based on the primary estimand:

- a) The first endpoint is
 - the change from baseline to Week 12 in percentage of time per day that CGM-derived values are >180 mg/dl (10 mmol/L)
- b) The second endpoint is
 - the change from baseline to Week 12 in duration of time in minutes per day that CGM-derived values are >180 mg/dl (10 mmol/L)

Of note, the primary estimand is described by the following attributes:

- Population: participants with T2D on a GLP-1 RA who may benefit from additional therapy. Further details can be found in Protocol Section 5.
- Treatment condition: treatment with tirzepatide regardless of changes to the background OAM. Further details on study treatment can be found in Protocol Section 6.
- Intercurrent events of interest: "Treatment discontinuation for any reason" and "Initiation of prohibited medication" will be addressed using the following strategies:
 - As if participants stay on the treatment (hypothetical strategy)
 - As if participants did not receive prohibited medication (hypothetical strategy).
- Population-level summary: Mean HbA1c change from baseline

Rationale for estimand: Estimating the effect of study intervention without confounding from prohibited mediations or treatment discontinuation.

2) The second clinical question of interest is for the secondary objective regarding fasting serum glucose levels:

What is the change in fasting serum glucose (FSG) from baseline to Week 12 in participants with T2D, regardless of changes in background OAM, and assuming that participants continue to take treatment without use of prohibited medication?

The endpoint corresponding to this question is the change from baseline to Week 12 in FSG.

3) The third clinical question of interest is for the secondary objective regarding weight:

What is the change in weight from baseline to Week 12 in participants with T2D, regardless of changes in background OAM, and assuming that participants continue to take treatment without use of prohibited medication?

The endpoint corresponding to this question is the change from baseline to Week 12 in weight.

1.2. Study Design

SURPASS-SWITCH-2 is a study to assess the changes in glycemic control when switching from a stable dose of a GLP-1 RA directly to tirzepatide 5 mg in participants with T2D. It has the following main design attributes:

- Phase 4 study
- Multicenter, single arm
- Open label
- The study consists of 2 periods:
 - Screening period: 3 weeks, starting from Visit 1 to Visit 2.
 - Treatment period: 12 weeks, starting from Visit 2 to Visit 5, where Visit 2 (on Week 0) and Visit 5 (on Week 12) are fasting visits.
- No dose escalation will be employed during the trial. The goal is to initiate tirzepatide at 5 mg on Visit 2 (on Week 0) and maintain until Visit 5 (on Week 12).
- The study will enroll approximately 150 participants.

Treatment Initiation			End of Treatment
Continue Baseline GLP-1 RA	Tirzepatide	5 mg SC QW	
CGM Assessment	CGM Assessment	8	CGM Assessment 12
Period I: 3-week Screening	Period II: 1 Treatment	2-week period	>

2. Statistical Hypotheses

For the primary estimand with primary endpoint, mean change in HbA1c percentage from baseline to Week 12, the following hypothesis is planned to be tested for tirzepatide 5 mg. Let the mean treatment difference be defined as μ = mean of ([HbA1c percentage at Week 12] – [baseline HbA1c percentage]), the statistical hypotheses are formulated as follows:

H₀:
$$\mu \ge 0.0$$
 vs. H_a: $\mu < 0.0$

Operationally the hypothesis will be evaluated by 2-sided test, at a 2-sided alpha level of 0.05.

2.1. Multiplicity Adjustment

Multiplicity adjustment will not be implemented in this study.

3. Analysis Sets

For the purposes of analysis, the following analysis sets are defined:

Population/Analysis Set	Description
Screened population	All participants who signed informed consent
Modified intent-to-treat population (mITT)	• All participants who are exposed to at least 1 dose of study intervention
Efficacy Analysis Set (EAS)	• This analysis set will be used to estimate the efficacy estimand for the primary objective, and for all other (secondary, exploratory) endpoints.
	• Data obtained during the treatment period from the mITT population, excluding (1) participants who were inadvertently enrolled* and (2) data after permanent discontinuation of treatment or initiation of prohibited medication.
Safety Analysis Set (SS)	• This analysis will be used to assess the safety of study treatment
	• Data obtained during the Treatment Period from the mITT population, regardless of adherence to treatment or initiation of prohibited medication.

* An inadvertent enroller refers to a subject who does not meet inclusion/exclusion criteria but receives study intervention.

4. Statistical Analyses

4.1. General Considerations

Statistical analysis of this study will be the responsibility of Lilly or its designee.

Any change to the data analysis methods described in the protocol will require an amendment *only if* it changes a principal feature of the protocol. Any other change to the data analysis methods described in the protocol, and the justification for making the change, will be described in the statistical analysis plan or clinical study report. Additional exploratory analyses of the data will be conducted as deemed appropriate.

Nominal significance levels:

All tests of treatment effects will be conducted at a 2-sided alpha level of 0.05, unless otherwise stated, and all confidence intervals will be given at a 2-sided 95% level.

Timing of Primary Analysis:

Primary analysis will be performed at database release after Last Participant Last Visit (LPLV).

Definition of baseline:

Baseline is defined as the last non-missing measurement recorded on or before the date/time of first dose. If the measurement time is not specified, it is assumed that any measurement taken on the date of first dose occurred prior to dosing.

Populations for analysis:

- Analyses will use the EAS to evaluate the primary efficacy estimand for all (secondary and exploratory) endpoints.
- Safety analysis will be performed on the SS.

Pooling of data:

Study data will be pooled across centers.

Analysis Windows:

Visit windows will be defined for by-visit summary and analysis purposes. Summary data such as adverse events and concomitant medications which are not reported by visit will not use visit windows. Visit labels will be assigned to each post-baseline record based on the windows or intervals for study day relative to the date of first dose. A record with the study day closest to the target visit day (week \times 7 days + 1) will be chosen when multiple records fall in the same visit window. In case of a tie, the record with the earlier date will be chosen. If Day 1 is missing, the closest visit on or before the date of first dose will be used as baseline. All visits will be included in the summary tables for worst post-baseline values.

All efficacy and safety analyses will be based on the visit windows in Table 1.

Study Day Relative to First Dose	Visit	Target Day
Study day ≤ 1	Baseline	1
$2 \leq study \ day \leq 43$	Week 4 (Visit 3)	29
$44 \leq \text{study day} \leq 81$	Week 8 (Visit 4)	57
$82 \leq study \ day \leq 88$	Week 12 (Visit 5)	85

Table 1.Visit Windows

General details of obtaining CGM-derived endpoints:

Participants will wear the study-provided CGM sensor to complete three 14-day sessions. The 14-day session should be conducted over the period indicated below:

- 1) Right after Visit 1, ideally Weeks -3 and -2.
- 2) Before Visit 3, ideally Weeks 3 and 4.
- 3) Before Visit 5, ideally Weeks 11 and 12.

Compliance is defined as the percentage of expected data that are actually collected (i.e., number of actually collected measurements / number of expected measurements \times 100%). For each of the session, the compliance must reach at least 70%, which equals to at least 10 out of 14 days. If a participant fails to reach the 70% compliance threshold on the session before Visit 3, the participant can attempt another session right after Visit 3 (ideally Weeks 5 and 6). CGM data collected from a non-compliant session will not be included in efficacy analysis.

CGM measurements over the 14-day session will be downloaded from the sensor on Visits 2, 3 (or 4 if non-compliance occurs), and 5, and are used to compute CGM-derived endpoints.

General statistical methods:

Summary statistics for continuous measures will include n, mean, standard deviation, median, minimum, and maximum. Categorical data (including categorized continuous measures) will be described using the sample size, participant count and percentage in each category. For the summary statistics of all numerical variables unless otherwise specified, minimum and maximum will be displayed to the same level of precision as reported. Mean and median will be displayed to one level of precision greater than the data collected. Standard deviation / standard error will be displayed to two levels of precision greater than the data collected as the data collected. P-values will be rounded to three decimal places. If a P-value is less than 0.001 it will be reported as '<0.001.' If a P-value is greater than 0.999 it will be reported as '>0.999.'

Data will be displayed in all listings sorted by participant ID. Participants will be identified in the listings by the participant identification number concatenated with the investigator number.

When count data are presented, the percentage will be suppressed when the count is zero in order to draw attention to the non-zero counts. A row denoted "Missing" will be included in count tabulations where specified on the shells to account for dropouts and missing values. The denominator for all percentages will be the number of subjects in that treatment within the analysis set of interest, unless otherwise specified.

The analysis model to make comparisons within treatment relative to continuous measurements assessed over time will be an MMRM with terms for:

- Visits, as fixed effects
- Baseline HbA1c ($\leq 8.0\%$, > 8.0%), as a covariate
- Baseline measurement, as a covariate

For analyses of HbA1c, continuous baseline HbA1c will be included in the model instead of baseline HbA1c category. An unstructured covariance structure will model the relationship of within-participant errors.

Logistic regression may be used to examine the within-treatment effect from baseline at 12 weeks in binary efficacy outcomes. The negative binomial regression model will be used to measure the within-treatment effect of discrete count measures if deemed appropriate.

Summary of intercurrent events:

The number of participants who experience an intercurrent event will be summarized in a table by event type (treatment discontinuation for any reason, or initiation of prohibited medication) and visit. For each visit, the number of intercurrent events which happened before or during the measurements taken on that visit will be calculated, excluding the events which happened during or before the measurements taken at the previous visits.

Furthermore, the number of participants without any intercurrent events will be presented by visit too. At each visit the number and percentage of participants without intercurrent events will be shown.

All analyses will be conducted using SAS Version 9.4 or higher.

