### Fasting visits

Participants should fast at least 8 hours without eating, drinking (except water), or performing any significant physical activity before the visit. If a participant attends a fasting visit in the non-fasting state, the sample should still be collected, and reschedule the fasting laboratory sample collection. This will not be considered a protocol deviation.

Study 18F-MC-GPIL	Period I -   Screening	Period II -	Treatment	Period			Comments
Visit Number	1	2	3	4	5	ED	ED = early discontinuation
Week Relative to Study Intervention Start	-3	0	4	8	12		
Visit Interval Tolerance (Days)	+3/-7	0	±3	£±	±3		Flexibility is built into the screening visit to ensure adequate CGM session and appropriate timing for stopping the baseline GLP-1 RA and initiating tirzepatide at Visit 2; see Section 4.1.1.
Fasting Visit		Х			Х	Х	
Informed consent	Х						The informed consent form must be signed before any protocol-specific tests or procedures are performed. See Section 10.1.3 for additional details

ப	
Ξ	
5	
J	
H	
2	
Ē	
$\mathbf{I8}$	

Study I8F-MC-GPIL	Period I - Screening	Period II -	Treatment	Period			Comments
Visit Number	1	2	3	4	2	ED	ED = early discontinuation
Week Relative to Study Intervention Start	-3	0	4	8	12		
Visit Interval Tolerance (Days)	+3/-7	0	±3	±3	+3		Flexibility is built into the screening visit to ensure adequate CGM session and appropriate timing for stopping the baseline GLP-1 RA and initiating tirzepatide at Visit 2; see Section 4.1.1.
Fasting Visit		Х			Х	Х	
Inclusion and exclusion criteria, review and confirm	Х	Х					Confirm inclusion and exclusion criteria prior to administration of first dose of study intervention.
Demographics	Х						Includes ethnicity (where allowed), year of birth, sex, and race.
Preexisting conditions and medical history, including relevant surgical history	Х						Collect all conditions ongoing and relevant past surgical and medical history.
Prior treatments for indication	Х						Add details of T2D medication, which includes medications used for T2D since diagnosis.
Substance use (alcohol, caffeine, tobacco use)	Х						
Concomitant medications	Х	Х	Х	Х	Х	Х	See Section 6.8.

PIL	
Q	
MC	
8F-]	

Study 18F-MC-GPIL	Period I - Screening	Period II -	Treatment	Period			Comments
Visit Number	1	2	3	4	5	ED	ED = carly discontinuation
Week Relative to Study Intervention Start	-3	0	4	8	12		

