Visit Interval Tolerance (Days)	+3/-7	0	±3	±3	±3		Flexibility is built into the screening visit to ensure adequate CGM session and appropriate timing for stopping the baseline GLP-1 RA and initiating tirzepatide at Visit 2; see Section 4.1.1.
Fasting Visit		Х			Х	Х	
Study intervention injection training with demo device		Х					Train participant with demo device prior to initial injection.
Review hypoglycemic events collected in the diary		Х	Х	Х	Х	Х	
Participant Diary							
Participant diary dispensed	Х	Х	Х	Х			Diary includes blood glucose values, collection of intervention administration, information on dosing date/time, and hypoglycemia. See Section 8.1.
Diary compliance check		Х	Х	Х	Х	Х	
Diary return		Х	Х	Х	Х	Х	
Laboratory Tests and Sample Collections							
Hematology	Х						
Hemoglobin A1C (HbA1c)	Х	Х	Х	Х	Х	Х	

GPIL	
l	
I8F-N	

Study 18F-MC-GP1L	Period I -   Screening	Period II -	Treatment	Period			Comments
Visit Number	1	2	3	4	5	ED	ED = carly discontinuation
Week Relative to Study Intervention Start	-3	0	4	8	12		
Visit Interval Tolerance (Days)	+3/-7	0	±3	士3	±3		Flexibility is built into the screening visit to ensure adequate CGM session and appropriate timing for stopping the baseline GLP-1 RA and initiating tirzepatide at Visit 2; see Section 4.1.1.
Fasting Visit		Х			Х	Х	
Clinical chemistry	Х	Х			Х	Х	Includes glucose testing.
Lipid panel		Х			Х	Х	
Urinalysis	Х						
Serum pregnancy	Х						Only for WOCBP and females with a history of tubal ligation. See Section 10.4.2.
Urine pregnancy (local)		Х			Х	Х	Collect for WOCBP only. The result must be available prior to first dose of intervention. Perform additional pregnancy tests if there is clinical suspicion of pregnancy, or as required by local law or regulation.
Follicle stimulating hormone (FSH)	X						Optional; perform as needed to confirm postmenopausal status. See Section 10.4.
Calcitonin	Х						

ЪЦ
Ģ
1Ċ
[8F-N

Study I8F-MC-GPIL	Period I - Screening	Period II -	Treatment	Period			Comments
Visit Number	1	2	3	4	5	ED	ED = early discontinuation
Week Relative to Study Intervention Start	-3	0	4	8	12		
Visit Interval Tolerance (Days)	+3/-7	0	±3	±3	±3		Flexibility is built into the screening visit to ensure adequate CGM session and appropriate timing for stopping the baseline GLP-1 RA and initiating tirzepatide at Visit 2; see Section 4.1.1.
Fasting Visit		Х			Х	Х	
Estimated glomerular filtration rate (eGFR)	Х						Calculate using CKD-EPI method.
Urinary albumin/creatinine ration (UACR)	Х						

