### **Period II: Treatment Period**

### Visit 2 Treatment Initiation

Participants arrive to the clinic in the fasting state. See Section 6.1 for intervention details.

This is the general flow for Visit 2:

- Participant returns screening CGM sensor for compliance review and data upload
- Study personnel confirm enrollment criteria
- Study personnel complete all required visit procedures, including the collection of vital signs, all baseline procedures, and sample collection, and
- Treatment initiation for eligible participants

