### First tirzepatide dose

Study personnel will observe as the participant injects the first dose of tirzepatide. The remaining injections will occur at participant's home. The date and time of the first dose of tirzepatide should be recorded on the CRF. Additionally, all medication doses administered at home should be captured, including date and time, in the participant's diary and subsequently recorded in the CRF.

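### SAP 4.1's closest-day rule has no fasting condition, so as written the FSG analysis can use a non-fasting glucose in place of its fasting repeat

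*SAP*

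**What the plan says.** - **Protocol 1.3, Fasting visits.** Visits 2, 5 and ED are the fasting visits. The instruction for non-fasting attendance is: "If a participant attends a fasting visit in the non-fasting state, the sample should still be collected, and reschedule the fasting laboratory sample collection". It adds: "This will not be considered a protocol deviation". That paragraph gives no latest day for the repeat.
- **Protocol 1.3, clinical chemistry row.** Samples are scheduled at Visits 1, 2, 5 and ED, with the comment "Includes glucose testing". None is scheduled at Visits 3 or 4.
- **SAP 4.1, Analysis Windows and Table 1.** Post-baseline records are labelled by study day: Days 2-43 are Week 4, Days 44-81 Week 8 and Days 82-88 Week 12 (target Day 85). If several fall in one window, "A record with the study day closest to the target visit day" is taken, or the earlier of two equally close records. The scope is stated as: "All efficacy and safety analyses will be based on the visit windows in Table 1".
- **SAP 4.1, baseline.** Baseline is the latest available value up to the first dose. There is a fallback: "If Day 1 is missing, the closest visit on or before the date of first dose will be used as baseline".
- **SAP 4.4.1 and 4.4.2 (Table 2).** FSG is analysed as change to Week 12, with terms for visit, baseline HbA1c category and baseline FSG. No condition on fasting status is given.
- **SAP 4.6.4.1, Vital signs.** Vital signs, including weight, are summarised by nominal visit.

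**The concern.** The protocol foresees non-fasting attendance and deliberately produces two glucose records for one visit. The SAP's rule for choosing between two records looks only at the calendar. The fasting repeat is drawn later, so it often lies further from Day 85 than the sample it was meant to replace, and the rule then discards it.

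At stake is one secondary endpoint. If non-fasting values run higher, a non-fasting Week 12 value understates the fall in FSG and a non-fasting baseline overstates it. No poor conduct is needed for this to happen: a Visit 5 held exactly on Day 85 is enough.

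**Working it through.** **1. Reproduce Table 1.** Target day = week x 7 + 1, which gives 29, 57 and 85. The Visit 5 tolerance is 3 days either way: 85 - 3 = 82 and 85 + 3 = 88. Table 1 agrees, so a Visit 5 inside tolerance is labelled Week 12.

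**2. Apply the rule at Visit 5.** Let *a* (82 to 88) be the day of the non-fasting sample and *b* > *a* the day of the fasting repeat.

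- If *b* is 88 or less, both records are Week 12 candidates. The non-fasting one is used when |*a* - 85| is less than or equal to |*b* - 85|; equality is the tie, which goes to the earlier date.
- If *b* is 89 or more, the repeat has no label in Table 1 and the non-fasting record is the only candidate.

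Pairs with both days in the window: 7 x 6 / 2 = 21. The repeat is chosen for *a* = 82 with *b* = 83-87 (5 pairs), *a* = 83 with *b* = 84-86 (3) and *a* = 84 with *b* = 85 (1), so 9 in all. The non-fasting value is chosen in 21 - 9 = 12, three of them ties (82/88, 83/87, 84/86). For *a* of 85 or later, every repeat is further from Day 85, so the non-fasting value is chosen in 6 of 6. Example: non-fasting Day 85, fasting Day 87; the distances are 0 and 2, and Day 85 is used.

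| Repeat drawn | Day pairs | Non-fasting used | Repeat on Day 89 or later |
|---|---|---|---|
| Inside the window | 21 | 12 | 0 |
| Within 3 days (assumed) | 21 | 14 | 6 |
| Within 7 days (assumed) | 49 | 40 | 28 |

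These count combinations of days; they are not expected frequencies. The last two rows include repeats beyond the Visit 5 tolerance, and the documents do not say whether that tolerance binds the repeat.

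**3. Apply the rule at baseline.** Protocol 4.1.1 ends the Visit 2 flow with "Treatment initiation for eligible participants" and adds: "Study personnel will observe as the participant injects the first dose of tirzepatide".

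- Fasting repeat before the first dose: it is the latest pre-dose value and is correctly the baseline.
- Fasting repeat after the first dose: the non-fasting Visit 2 value is the baseline, and a repeat on Days 2-43 is labelled Week 4, where no glucose is scheduled.
- No Visit 2 glucose: the fallback reaches Visit 1, which has chemistry but is not a fasting visit.

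The documents do not say which of the first two would occur.

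**4. Look for another rule that resolves it.** The only other rule for several laboratory values within a visit, in the safety section (SAP 4.6.4.1), takes the worst value. It has no fasting condition either.

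**5. Illustrate the size (assumed inputs).** Shift in mean Week 12 FSG = fraction non-fasting x excess of a non-fasting value. With an assumed excess of 20 to 60 mg/dL:

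- 2%: 0.02 x 20 to 0.02 x 60 = 0.4 to 1.2 mg/dL
- 5%: 1.0 to 3.0 mg/dL
- 10%: 2.0 to 6.0 mg/dL

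**6. Early Visit 5 (minor).** Day 81 is 4 days from Day 85 and 24 from Day 57, yet Table 1 labels it Week 8. An FSG from such a visit becomes a Week 8 value that the schedule never planned. A Visit 5 weight on that day is Week 8 under SAP 4.1 but Visit 5 in the nominal-visit summary of SAP 4.6.4.1, although SAP 4.1 claims to govern all analyses.

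**The case against.** The best reply is that the endpoint is called fasting serum glucose, SAP 1.2 describes Visits 2 and 5 as fasting visits, and the repeat exists because a non-fasting draw does not serve. On that reading the closest-day rule chooses only among fasting records. SAP 1 also places output specifications in a separate document, which may filter on fasting status. This stands as evidence of intent and lowers confidence. It does not remove the gap: the one explicit selection rule covers all efficacy analyses and is silent on fasting.

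Second, the Visit 2 flow puts baseline sampling before treatment. That is fair. A reader might infer that a fasting repeat of Visit 2 is always lost; the documents do not support this, because a repeat before the first dose would be chosen.

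Third, a reader might infer that any fasting repeat of Visit 5 should simply count as Week 12. The documents do not support that either. At Visit 5 the investigator decides the move to other diabetes treatment, which may be the previous GLP-1 RA (Protocol 4.1.1), and the Schedule of Activities dispenses no study drug then. A later repeat may be off tirzepatide or on another agent, outside what the estimand and the Efficacy Analysis Set (EAS) allow.

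Fourth, SAP 4.3.2, carried over by 4.4.2, models change to scheduled visits. This can be read as already excluding a Week 8 FSG, but Table 1's labels do not say so. Only visits outside the 3-day tolerance are affected.

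**Conclusion.** The gap is real as a matter of text and limited in reach. As written, a non-fasting Visit 5 sample on Days 85 to 88 is always used in preference to its later fasting repeat, and 12 of 21 in-window day pairs go the same way. The baseline rule accepts a non-fasting Visit 2 value if the repeat follows the first dose, or a Visit 1 value if Visit 2 is missing.

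Confidence is moderate. The unseen specifications may already filter, the documents give no rate of non-fasting attendance, and the mg/dL shifts rest wholly on assumed inputs. Protocol 1.3 also counts significant physical activity as breaking the fast, so a non-fasting value need not be a fed one.

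A reader might infer that the FSG result will be biased, or that the primary result is threatened. Neither follows: the text permits the wrong choice without showing how often it would be made, and HbA1c does not depend on fasting. The early-visit labelling is a tidying matter and gives no general reason to prefer nominal visits to windows. The point is worth correcting because it is cheap and the situation is foreseen by the protocol.

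**What to change.** In SAP 4.1 and 4.4.1:

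1. State that FSG analyses, at baseline and at Week 12, use only samples recorded as fasting, and that this restriction is applied before the closest-day rule. The fasting repeat is then chosen in 21 of 21 in-window pairs instead of 9, subject to the existing EAS exclusions. Confirm that fasting status is recorded with each sample.
2. State that a fasting sample taken after the first dose to replace Visit 2 is neither a baseline nor a Week 4 value.
3. For a fasting repeat of Visit 5 after Day 88, state before database lock whether, and up to which day, it counts as Week 12. Accept it only if the participant has not permanently stopped tirzepatide or started prohibited medication; otherwise Week 12 FSG is missing.
4. Minor: do not enter an early Visit 5 FSG as a Week 8 value, and reconcile the scope statement in SAP 4.1 with the nominal-visit summaries in SAP 4.6.4.1.

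The cost is a few sentences and some missing FSG values, for example where no fasting sample precedes the first dose. If the separate specifications already filter on fasting status, the change only brings the SAP into line with them.
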